## **Study Drug and Administration**

### **Drug Supplies**

Film coated tablets – 5mg and matching placebo.

Ambrisentan is manufactured by Gilead Sciences Incorporated. The drug is marketed and supplied as 5 and 10mg film coated tablets. The tablets are different colors for the different dosages and are also labeled with the dose on the outside of the tablet. Matching placebo tablets are identical in appearance and are available in the 5 and 10mg forms. Ambrisentan will be administered as a tablet to all children that are able to take an oral tablet. In those that are unable to swallow a tablet, ambrisentan/placebo will be compounded as described below and administered as an oral suspension. A secondary study objective is to compare bioavailability of the tablet versus compounded formulation.

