## 4. Design and Procedures

This is a single-center, randomized, blinded PK study of ambrisentan in children ages  $\geq 24$  months and  $\leq 120$  months with single ventricle anatomy. There will be up to 20 subjects enrolled; 16 will receive ambrisentan and 4 will receive placebo. A small placebo control group is warranted to ensure that any treatment effect is not a result of post-operative improvement. Patients will be enrolled at the time of their routinely scheduled Fontan surgery.

**Initial Dose:** Oral ambrisentan 2.5 – 5 mg, single dose, once daily (nasogastric and gastrostomy tube administration will be considered only when a nasogastric or gastrostomy tube is already in place as part of routine post-operative care). Subjects will be randomized by Investigational Drug Services (IDS) to placebo (n=4) or oral ambrisentan (n=16) using permuted blocks. Subjects will receive either an oral suspension (2.5 or 5mg) or a 5mg tablet depending on their ability to swallow a tablet. To begin to ensure safety, the initial 5 subjects enrolled in the study (at least 4 active drug) will receive a dose of 2.5mg in a liquid suspension prepared by IDS. After enrollment of these subjects we will perform a preliminary PK/safety analysis and evaluate ambrisentan exposure. If the drug is well tolerated (no grade III or greater adverse events) and exposure is less than the target exposure of 500-800ng/mL, then we may increase the dose to 5mg/dL provided via tablet in those able to take a tablet or suspension for all others. If drug exposure is less than 100ng/mL then we will enroll additional study subjects to ensure that at least 16 study subjects achieve adequate drug exposure. If drug exposure is in the target range then we will continue to enroll study subjects to receive the 2.5mg suspension.

As summarized below, study drug will be discontinued for any grade 3 or greater adverse event. If this occurs then IDS will be permitted to unblind the study patient to allow for appropriate adverse event reporting. Drug administration will start on post-operative day #1 with initiation of oral feeds. Study drug/placebo will be prepared and delivered to the patient bedside by investigational drug services and administered orally. Subjects will continue on study drug for 3 days.

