### Compounding:

- All drug compounding procedures should be performed under a safe fume hood.
- During preparation of suspension, gloves and a mask should be worn.
- Crush 5mg tablet,
- Suspend in equal parts of Ora-plus (2.5 mL) and Ora-sweet (2.5 mL)
- Stability: the suspended dose must be administered within 4 hours of preparation.

Ambrisentan must be delivered to the patient room from the investigational drug service on the day of administration. A label containing the protocol number and patient number must be applied to the drug package or syringe. The exact time of study drug administration must be documented on the case report form. Vital signs will be recorded per standard post-operative protocol for the remainder of the study.

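### Section 5's tablet rule contradicts Section 4's 2.5 mg suspension rule by a factor of two for children who can swallow a tablet, and the compounding recipe gives no volume for a 2.5 mg dose

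*Combined protocol and SAP*

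**What the plan says.** Section 4 (Design and Procedures) sets the dose by cohort. For the lead-in, "the initial 5 subjects enrolled in the study (at least 4 active drug) will receive a dose of 2.5mg in a liquid suspension", made up by the investigational pharmacy (IDS). A preliminary PK and safety analysis follows. If there are no adverse events of grade III or above and exposure is below the 500–800 ng/mL target, the dose may go up, and only there do tablets enter the cohort rules: "then we may increase the dose to 5mg/dL provided via tablet" for children able to take one, with suspension for the rest. If exposure is already in the target range, later subjects stay on the 2.5 mg suspension. Ahead of these rules the same section has a general sentence: "Subjects will receive either an oral suspension (2.5 or 5mg) or a 5mg tablet depending on their ability to swallow a tablet".

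Section 5 (Drug Supplies) sets the formulation by ability to swallow: "Ambrisentan will be administered as a tablet to all children that are able to take an oral tablet". Children who cannot swallow a tablet get the compounded suspension. The study supply line names 5 mg tablets and matching placebo. No 2.5 mg tablet is listed. The same text makes a comparison of tablet and compounded bioavailability a secondary objective.

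Section 5 (Compounding) has one recipe. It begins "Crush 5mg tablet", suspends the tablet in 2.5 mL of each of two vehicles, and adds that "the suspended dose must be administered within 4 hours of preparation". It gives no volume to administer.

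**The concern.** The two sections give different instructions for the same child. Section 4 fixes both dose and formulation for the lead-in, and for everyone after it if exposure is in target. Section 5 fixes the formulation for every tablet-capable child, and with 5 mg tablets as the supply that also fixes the dose. Neither refers to the other and neither states an order of precedence.

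Two things depend on the lead-in dose being what Section 4 says it is. The first is the safety step itself, because tolerability at 2.5 mg is a condition for any increase. The second is the exposure result, which chooses between staying at 2.5 mg and increasing. With as few as four active subjects, one child on a different dose carries a quarter of the weight in that decision. Section 5 also has IDS strip patient identifiers before forwarding drug levels for PK analysis, and it does not say whether the dose given travels with the level.

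**Working it through.** **Inputs.** Lead-in dose 2.5 mg, and lead-in size 5 with at least 4 active (Section 4). Tablet strength supplied 5 mg (Section 5, Drug Supplies). Recipe: one 5 mg tablet in 2.5 mL + 2.5 mL (Section 5, Compounding). Lower limit of target exposure 500 ng/mL (Sections 4 and 5).

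**Step 1: the tablet-capable child on active drug, stage by stage.**

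| Stage | Section 4 | Section 5 | Ratio |
|---|---|---|---|
| First 5 subjects | 2.5 mg suspension | 5 mg tablet | 5 / 2.5 = 2 |
| Later, exposure in target | 2.5 mg suspension | 5 mg tablet | 5 / 2.5 = 2 |
| Later, dose increased (unit read as mg) | 5 mg tablet | 5 mg tablet | 5 / 5 = 1 |

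The sections agree only where the dose has been increased. The conflict is not confined to the lead-in.

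**Step 2: the child who cannot swallow a tablet.** Concentration = 5 mg / (2.5 mL + 2.5 mL) = 1 mg/mL.

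- Whole preparation: 5 mL × 1 mg/mL = 5 mg, which is 2.0 times the lead-in dose.
- Half of it: 2.5 mL × 1 mg/mL = 2.5 mg, which is 1.0 times the lead-in dose.

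The recipe can therefore yield 2.5 mg, but only through a measuring step that Section 5 does not write down.

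**Step 3: what a mixed lead-in could do to the exposure result.** This is an illustration. It assumes that exposure is proportional to dose, that the mean is the summary used, and that dose is not adjusted for. The documents state none of these. If k of n active subjects receive 5 mg in place of 2.5 mg, then

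apparent mean / mean at 2.5 mg = [(n − k) × 1 + k × 2] / n = 1 + k/n.

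- n = 4, k = 1: 1 + 1/4 = 1.25
- n = 5, k = 1: 1 + 1/5 = 1.20
- k = n: 2.00

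The documents do not say how many children could swallow a tablet, so the range is 1.00 (none) to 2.00 (all). With n = 4 and k = 1, a mean at 2.5 mg of 400 ng/mL would show as 400 × 1.25 = 500 ng/mL. Values from 400 to just under 500 would then be read as reaching the target, and the rule would keep the dose where it was.

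**Step 4: the bioavailability objective.** If exposure at 2.5 mg is in target and Section 4 governs, nobody receives a tablet and the comparison cannot be made. If Section 5 governs in that situation, a 5 mg tablet is compared with a 2.5 mg suspension, so formulation and dose change together.

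**The case against.** The best defence is that the specific rule overrides the general one. Section 4 addresses the first five subjects by number and gives them a dose and a formulation. Section 5's sentence is a general statement under a supplies heading and names no cohort. IDS prepares and delivers each dose and is told in Section 4 to make 2.5 mg for the lead-in, so a doubled dose would mean IDS passing over an explicit instruction. IDS also handles the drug levels, so the dose given need not be unknown. These points stand to the extent that they make a dosing error less likely. They do not remove the conflict. The protocol states no precedence, Section 5 speaks of all children without exception, and Section 4's own general sentence also turns on ability to swallow.

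Three stronger readings are tempting, and the documents do not support them:

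- A reader might infer that both Section 5 routes can give only 5 mg. The recipe makes a 1 mg/mL suspension from which 2.5 mg can be measured, and Section 4 names a 2.5 mg suspension among the preparations. The reference to a suspended dose sits in a stability instruction and does not direct that the whole volume be given. This is an omission, not a contradiction.
- A reader might take 5 mg/dL as a suspension strength and find it 20-fold below the recipe (1 mg/mL = 100 mg/dL; 100 / 5 = 20). The phrase concerns a dose given by tablet, and the same section writes the dose in mg elsewhere. It is a unit slip, and the ratio has no meaning.
- A reader might conclude that the interim exposure result would be uninterpretable. That requires mixed dosing to occur and the dose given to be unknown to the analyst. The documents establish neither.

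**Conclusion.** The contradiction is real and should be fixed. For a tablet-capable child on active drug, Sections 4 and 5 give doses that differ two-fold, both in the lead-in and afterwards if exposure is in target. The factor of two rests on a literal reading of Section 5 and on 5 mg being the tablet supplied. It has practical effect only if at least one such child is enrolled at one of those stages, which the plan itself anticipates by providing tablets. The missing volume in the recipe is a lesser gap, and the concentration unit is editorial. The distortion of the interim result is conditional: 1.20 to 1.25 times for one child, under the assumptions shown, and none if Section 4 is followed or the dose is accounted for. No sample size, power or error-rate figure is involved. This review takes no position on which dose or formulation rule is correct.

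**What to change.** Reconcile Section 4 with the Drug Supplies and Compounding text of Section 5:

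1. Make the tablet rule agree with the dose cohorts, stating for each cohort which formulation a tablet-capable child receives, or state which section governs.
2. For each dose the protocol uses, give the preparation and the volume to administer.
3. Write the increased dose in one mass unit throughout.
4. State what the reconciled rule means for the secondary comparison of tablet and suspension: whether any subjects will receive tablets, and whether the two formulations will be given at the same dose.

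The investigators decide the content of items 1 and 2. The cost is a wording amendment and a matching pharmacy instruction. Sample size does not change. The bioavailability comparison may need to be restated or dropped, depending on how item 1 is settled.

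### Sections 4 and 5 give conflicting dose and formulation rules for a child who can swallow a tablet; following Section 5 gives at least twice the 2.5 mg that Section 4 sets, and no volume is stated for the suspension

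*Combined protocol and SAP*

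**What the plan says.** Section 4 (Design and Procedures, Initial Dose) sets the dose by stage. The first 5 subjects, at least 4 of them on active drug, "will receive a dose of 2.5mg in a liquid suspension prepared by IDS". A preliminary PK and safety analysis follows. If there has been no adverse event of grade III or above and exposure is below 500-800 ng/mL, the dose may be raised to 5 mg, as a tablet for those able to take one and as suspension for the rest. Otherwise: "If drug exposure is in the target range then we will continue to enroll study subjects to receive the 2.5mg suspension". Neither 2.5 mg rule depends on swallowing ability. Earlier in the same paragraph, however, subjects are assigned a suspension (2.5 or 5 mg) "or a 5mg tablet depending on their ability to swallow a tablet".

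Section 5 (Drug Supplies) sets the formulation by swallowing ability alone. Its supply line reads "Film coated tablets – 5mg and matching placebo"; the text below it names 5 and 10 mg as the marketed strengths. It then states "Ambrisentan will be administered as a tablet to all children that are able to take an oral tablet", and "In those that are unable to swallow a tablet, ambrisentan/placebo will be compounded as described below and administered as an oral suspension". It makes no exception for the first 5 subjects or for any later stage. It also names a comparison of tablet and compounded bioavailability as a secondary objective.

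Section 5 (Compounding) has one recipe: "Crush 5mg tablet", then suspend it in 2.5 mL of each of two vehicles. It refers to the product as a dose and gives no volume to draw up. On records, it says "The exact time of study drug administration must be documented on the case report form", and the label it describes carries the protocol and patient numbers.

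**The concern.** For a child in the first cohort or in the in-target branch who can swallow a tablet, Section 4 calls for a 2.5 mg suspension and Section 5 calls for a tablet. Since no 2.5 mg tablet is listed, the disagreement over formulation is also a disagreement over dose.

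Two things are at stake. The first is safety: Section 4 presents the 2.5 mg start as an early safety step, and the Section 5 rule would bypass it for tablet-takers. The second is the interim decision: exposure in the first cohort, together with tolerability, determines whether the dose may rise. If some of those children received 5 mg and the result were read as a 2.5 mg result, an exposure below target could look adequate. In the non-compartmental analysis, apparent clearance is dose divided by AUC, so entering 2.5 mg for a child given 5 mg would halve that child's estimate (2.5/5 = 0.5).

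**Working it through.** **Inputs.** Section 4: 2.5 mg suspension for the first 5 subjects and the in-target branch; at least 4 active children in the first 5; target 500-800 ng/mL. Section 5, Drug Supplies: 5 mg tablet as study supply; 5 and 10 mg marketed. Section 5, Compounding: one 5 mg tablet in 2.5 + 2.5 mL.

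**Step 1: can the 2.5 mg dose be reached under each rule?**
- Tablet rule: 5/2.5 = 2.0 times the Section 4 dose with the smallest tablet named. The 2.5 mg dose cannot be reached.
- Suspension: 5 mg/(2.5 + 2.5 mL) = 1 mg/mL. The whole 5 mL holds 5 mg (2.0 times); 2.5 mL holds 2.5 mg (1.0 times). The recipe is compatible with 2.5 mg but does not specify it.

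**Step 2: what could this do to the interim reading?** The documents give neither the number of tablet-takers nor the summary statistic on which the decision rests. Assume dose-proportional peaks, equal bioavailability of tablet and suspension, a decision based on the mean, and 4 active children. If k of the 4 receive 5 mg, the mean is multiplied by (4 - k + 2k)/4 = 1 + k/4. A true 2.5 mg mean M reads as in target when 500 ≤ M(1 + k/4) ≤ 800, and it is truly below target when M < 500.

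| k | Multiplier | 500/multiplier | 800/multiplier | Below-target means that read as 500-800 ng/mL |
|---|---|---|---|---|
| 0 | 1.00 | 500 | 800 | none |
| 1 | 1.25 | 400 | 640 | 400-500 |
| 2 | 1.50 | 333 | 533 | 333-500 |
| 3 | 1.75 | 286 | 457 | 286-457 |
| 4 | 2.00 | 250 | 400 | 250-400 |

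For k = 3 and 4 the upper limit falls below 500. True means of 457-500 (k = 3) or 400-500 (k = 4) would read above 800, up to 500 × 1.75 = 875 and 500 × 2 = 1000. Section 4 states no action for a reading above target.

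With 5 active children the multiplier is 1 + k/5, and the ranges are 417-500, 357-500, 312-500, 278-444 and 250-400 ng/mL for k = 1 to 5.

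**Step 3: in-target branch.** If 2.5 mg gives 500-800 ng/mL, then under the same proportionality and bioavailability assumptions a 5 mg tablet projects to 2 × 500 = 1000 up to 2 × 800 = 1600 ng/mL, above the plan's upper limit of 800.

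**Step 4: the bioavailability objective.** If the in-target branch of Section 4 is followed as written, nobody in it receives a tablet, so the comparison named in Section 5 cannot be made there.

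**The case against.** The best defence is that Section 4 is the more specific text. It names the first 5 subjects, fixes their dose and formulation, and has the pharmacy service prepare it; its swallowing sentence can be read as a list of available formulations, with the staging rule following at once. On that reading, Section 5 is general background. This makes an error less likely, but it does not settle the conflict: Section 4 never says that it overrides Section 5, and Section 5 speaks of all children. Nor does that reading supply the missing volume or rescue the bioavailability objective in the in-target branch.

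Several stronger readings are tempting and should not be drawn.

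- *The recipe itself doubles the dose.* It does not: at 1 mg/mL, half the preparation holds 2.5 mg. The defect is the unstated volume, made worse by wording that treats the whole preparation as a dose.
- *The interim will be misread.* That requires an active first-cohort child who is given a tablet or the full suspension despite Section 4, and an analyst who does not know it. The documents show neither.
- *The dose given is not recorded.* The protocol names time of administration and does not list mg given, and Section 5 (Rationale for Dose Selection) has levels forwarded without identifiers and does not say that dose or formulation goes with them. But the pharmacy service knows what it dispensed, Section 14 tabulates laboratory data by dosage group, and the formulation comparison needs formulation by subject. The case report form and any pharmacy manual are not part of the documents.
- *Exposure alone decides the interim step.* Section 4 also requires tolerability, and it says only that the dose may be raised.
- *Every tablet-taker in the in-target branch would exceed 800 ng/mL.* The projection applies a cohort range under unstated assumptions; it does not describe each child.

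**Conclusion.** The contradiction stands on the text alone and needs no assumption: a child able to swallow a tablet cannot be treated under both sections in the first cohort or the in-target branch, and following Section 5 gives at least twice the dose in Section 4. The missing volume is a second, separate gap. Because these are conflicting dosing instructions for post-operative children at the step meant to protect them, they must be reconciled before the plan is used.

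The effect on the interim analysis is a conditional risk. Its size runs from none to a doubling of mean exposure, depending on a number of misdosed children that the documents do not give, and it rests on the four assumptions listed in the working. The 1000-1600 ng/mL projection rests on two of them, dose proportionality and equal bioavailability.

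**What to change.** Reconcile Section 4 (Initial Dose) with Section 5 (Drug Supplies and Compounding) so that each stage (first 5 subjects, in-target branch, escalated branch) carries one consistent dose and formulation instruction, and state the volume of suspension to administer for each dose level in use. Which dose and formulation to use is for the clinical team.

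On the data side, record the mg and formulation actually given at each administration, send them with the de-identified levels, use the actual dose in the non-compartmental analysis, and interpret interim exposure by the dose received.

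The cost is protocol and pharmacy wording plus one record field, with no added patients or procedures. There is one real consequence: if the in-target branch of Section 4 is kept, the tablet-versus-compounded bioavailability objective cannot be met in that branch, so that objective must be reconciled as part of the same amendment.

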### Compounding:

- All drug compounding procedures should be performed under a safe fume hood.
- During preparation of suspension, gloves and a mask should be worn.
- Crush 5mg tablet,
- Suspend in equal parts of Ora-plus (2.5 mL) and Ora-sweet (2.5 mL)
- Stability: the suspended dose must be administered within 4 hours of preparation.

Ambrisentan must be delivered to the patient room from the investigational drug service on the day of administration. A label containing the protocol number and patient number must be applied to the drug package or syringe. The exact time of study drug administration must be documented on the case report form. Vital signs will be recorded per standard post-operative protocol for the remainder of the study.

## **6. Selection of Subjects:**

### **Inclusion Criteria**

1. Age  $\geq$  24months and  $\leq$  120 months.
2. Congenital heart disease with underdevelopment of the right or left ventricle.
3. Presenting for elective Fontan (total cavopulmonary anastomosis) single ventricle palliation.
4. Availability and willingness of the parent/legal guardian to provide written informed consent

### **Exclusion Criteria**

1. History of serious adverse event related to ambrisentan administration.
2. History of ambrisentan exposure within 48 hours of the study.
3. Presence of pulmonary venous obstruction.
4. Treatment with cyclosporin
5. Any of the following – as determined by the attending physician
  - a. Significant hemodynamic instability
  - b. Sepsis.
6. Renal failure defined as serum creatinine  $>$  2 times higher than the upper limit of normal.

7. Atrial hypertension defined as a common mean atrial pressure  $> 12$  mm Hg via direct measurement (central line) or a Fontan mean pressure  $> 22$  mm Hg in a patient with no atrial line.

## **7. Subject recruitment and compensation:**

Children presenting for elective Fontan surgery age  $\geq 24$  months and  $\leq 120$  months will be identified by the research staff and screened for eligibility. A caregiver known to the family will introduce the study. If the family is interested in participating, study staff will then approach families to review the study and get written consent at a pre-surgical clinic visit or at the time of pre-surgical cardiac catheterization. Approval by the subject's healthcare provider will be obtained prior to enrollment. We will consent up to 50 subjects with the goal of achieving up to 20 evaluable subjects. There will be no compensation for subject participation.

## **8. Consent Process:**

The research staff will conduct the consent process as outlined by GCP guidelines. Consent will be obtained from each child's parent or legal guardian when they are identified by study staff as an eligible candidate for study enrollment. Consent is indicated on the study-specific consent form with the signature of the parent or guardian. The process will take about 1 hour and the parent/guardian will be allowed as much time as they need to decide whether or not to enroll their baby in the study.

